Once approved for participation in the study all participants will undergo a brief instructional class on how to operate the HMD and will be allowed sufficient time to become comfortable with its use. We expect approximately 5-10 minutes to be required for this portion of the study. Once familiar with the use of the VR headset, participants will be asked to randomly draw an envelope from a container. This envelope will contain a block and sequence number. The block and sequence number will be the subject ID and will correspond to a predetermined number set on a separate document that will determine if the participant will use the HMD during venipuncture or not. The screener will not have immediate access to the list showing which group the participant will be assigned to. One member of the study team will be present in the lab room to ensure the participant uses the VR headset (or not) according to what is randomly drawn. This member of the research team will have the list showing whether or not the participant is assigned to the control arm or the experimental arm. The participants will then proceed to the specimen room to undergo venipuncture.

Venipuncture for both groups will occur in the non-dominant arm. The reasoning for this is that the Oculus Go requires one free hand to use a controller. This will ensure that the individuals participating are able to effectively use the device. Those unable to undergo venipuncture in the non-

dominant arm will undergo venipuncture in the dominant arm instead and will use the Oculus Go controller with their non-dominant hand.

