As this study will utilize and Intention to Treat (ITT) methodology, all enrolled subjects will be included in the final data analysis.

11.2 Sample Size:

60

11.3 Total number of subjects requested (including records and specimens):

60

11.4

If you are recruiting by study arm, please identify the arms of the study and how many subjects will be enrolled in each arm

Control (standard of care) - 30

Experimental (standard of care plus virtual reality) - 30

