11.5 Please provide a justification for your sample size

A study performed by Todd et al 1995 and a later validation study by Gallagher et al 2001 both found that a minimum clinically significant change in pain as measured on the VAS is 13mm. Both studies found that the change in pain reported as "a little more pain" or "a little less pain" after intervention averaged to 13mm. Both studies also found that the standard deviation of change in pain reported on the VAS as "a little more pain" or "a little less pain" was 17mm.

Since the t-test will be used at the end of the study to determine if the effects are statistically significant, the E/S ratio (expected effect size divided by the standard deviation of the outcome variable) was used to determine the sample size. The E/S ratio is being estimated based on the studies cited above. The expected effect size (13mm) divided by the standard deviation (17mm) =0.76. To ensure a 2-sided α 0.05 and β 0.20, a minimum of 27 subjects are required for each arm. This is based on a sample size calculator created by Dhand et al as well as appendix 6A of *Designing Clinical Research* authored by Hulley et al.

Although a total of only 54 participants is required for this study to be effectively powered, we're requesting 60 to account for a potential dropout rate of 10%.

Minitab software will be utilized for final data analysis.

11.6 Data Analysis Plan: Complete description: Background, Objectives, Design, Step by Step how the project is going to be done, Data analysis plan:

The primary outcome be measured as the average pain rating between the two groups as measured on the VAS. The t-test will be used to compare the two groups to determine if the difference is statistically significant. The difference between the two groups should be at least 13mm to be considered clinically significant.

The preprocedural anxiety will also be measured using the VAS and the average difference will be reported in the data, although a minimum clinically significant score is not available.

Since participants will be randomly assigned to each study arm, it will be impossible to insure an even spread of ages between the two study arms. It may be possible that pain perception changes with age, and since this study will include ages 18-50, data tables comparing the average changes between those in different age groups (i.e. 18-25, 26-33, 34-41, 42-50). A separate subgroup analysis will be performed comparing different age subgroups.

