possession of the PI. When not in the PI's possession it will be secured in a locked office. The de-identified electronic data will be stored on the attached Excel spreadsheet. Paper copies will be shredded once data has been transferred. Once the study is complete the electronic documents will be maintained on the primary investigator's CAC-enabled/password protected government computer until the computer is turned in upon PCSing and then deleted.

14.4 Potential Benefits:

Describe any real and potential benefits of the research to the subject and any potential benefits to a specific community or society

If the individuals in the research are considered experimental subjects (per 10 USC 980), and they cannot provide their own consent, the protocol must describe the intent to directly benefit all subjects

The subjects in the experimental group will potentially benefit from this study via reduction in anxiety and pain control, but will not directly benefit from this study in any other way. If Virtual Reality is shown to decrease pain intensity and anxiety levels with venipuncture, it may be offered in the lab setting, clinic setting, emergency room setting, or deployed setting to improve the care that can be provided.

14.5 Privacy for Subjects:

Describe the measures to protect subject's privacy during recruitment, the consent process, and all research activities, etc.

During the screening process no PHI will be collected. The participant's name and signature will be on the consent form, but will not be linked to any PHI. The screening questionnaire will contain age and gender, and will ask several questions about health, but will not be linked to the consent form and therefore will not contain PHI. This will be performed in a private room with only the member of the study team collecting the data present. Once gathered, the data will be stored in electronic form on a secure CAC-enabled/password protected government computer that will be in the possession of the PI. After paper documents are transferred electronically they will be shredded, the electronic documents will be kept for 3 years and then deleted.

14.6 Incidental or Unexpected Findings:

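### Section 11.6 calls an even age spread between arms unattainable, but age is recorded before allocation, and the plan controls for it neither in allocation nor in the primary t-test

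*Combined protocol and SAP*

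**What the plan says.** Section 11.6 (Data Analysis Plan) states that, with random assignment, "it will be impossible to insure an even spread of ages between the two study arms". It then allows that pain perception may change with age. Its response is a set of tables for four age bands (18–25, 26–33, 34–41, 42–50) and a separate subgroup analysis comparing them. Under both Section 11.1 and Section 11.6 the primary comparison is a t-test on mean VAS pain, with no covariate.

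On timing, Section 14.5 says "The screening questionnaire will contain age and gender". Sections 10.1 and 13.1 place screening and the eligibility decision, which itself depends on age, before the envelope step.

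On mechanism, Section 10.1 has each participant draw at random from a container. Of the envelope it says "This envelope will contain a block and sequence number", and this number is looked up on a list prepared beforehand. No block size is given, and the blocks are not tied to age. The arms in Section 11.4 are "Control (standard of care) - 30" and "Experimental (standard of care plus virtual reality) - 30".

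**The concern.** Random assignment does not rule out balance on a factor known at baseline; stratified allocation exists for that purpose. What it needs is mostly in place: age is known in time, and there are envelopes, block numbers and a prepared list. Age is the only factor that the analysis plan names as possibly unbalanced, yet it is controlled neither at allocation nor in the primary comparison. Age-band tables and a subgroup analysis describe results by age; they do not remove the contribution of an age gap from the overall difference in means.

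Two things are at stake: the precision and readability of the primary comparison if age does matter for pain, and the usefulness of the age-band tables, where about 15 people per band can split unevenly between arms. Allocation cannot be changed once people are enrolled, and Section 16.1 expects data collection to last only 3–4 days.

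**Working it through.** **The plan's own figures.** Section 11.5 states: "The expected effect size (13mm) divided by the standard deviation (17mm) =0.76" and "To ensure a 2-sided α 0.05 and β 0.20, a minimum of 27 subjects are required for each arm".
- n per arm = 2 × (1.960 + 0.842)² × (17/13)² = 26.84, so 27. This reproduces by the normal approximation. (With the ratio rounded to 0.76 it is 27.2, so 28.)
- 54 / 0.90 = 60, so the dropout allowance also reproduces.

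The documents state no figure for age imbalance, so the rest is new calculation on stated assumptions.

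**Inputs.** From the documents: ages 18–50, 30 per arm, pain SD 17 mm, target difference 13 mm. Assumed, because the documents do not give them: the age distribution, the block size (four) and the age–pain correlation.

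**Chance gap in mean age, ages uniform from 18 to the end of year 50.**
- SD of age = 33/√12 ≈ 9.52 years.
- SD of the between-arm difference in mean age, unstratified = 9.52 × √(2/30) = 2.46 years.
- A split at 34 halves the SD of age within each stratum (ratio 0.50), so the limit is 2.46 × 0.50 = 1.23 years. Simulation with blocks of four opened in order gives about 1.3 years; incomplete last blocks account for the rest.
- The reduction is 46–48%. The chance of a gap above 3 years falls from about 21–22% to 2%, and above 4 years from about 10% to about 0.1%.

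**Other assumed age shapes on 18–50** (simulated SD of the gap in years, unstratified → stratified, blocks opened in order):

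| Assumed shape (share aged 34 or over) | Cut at 34 | Cut at median |
|---|---|---|
| Young (24%) | 1.88 → 1.13 (40%) | 1.88 → 1.07 (43%) |
| Very young (7%) | 1.40 → 1.11 (21%) | 1.40 → 0.90 (35%) |
| Peaked in the middle (53%) | 1.62 → 0.95 (42%) | 1.62 → 0.93 (43%) |
| Older (79%) | 1.87 → 1.18 (37%) | 1.87 → 1.06 (43%) |

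Over all shapes, including uniform, the reduction is about 35–48% with a median cut and about 20–48% with a cut at 34.

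**If the container draw is kept.** With two age-specific containers of 60 envelopes, each still drawn at random, the reduction is about 15–20% with a median cut (2–20% over all scenarios), and 30:30 is no longer guaranteed. Most of the gain comes from opening the blocks in order.

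**Age bands.** Assume 15 people in each of the plan's four bands. Under an unstratified 30:30 list, the chance that at least one band splits 5:10 or worse is about 58%. With two strata (18–33 and 34–50) in blocks of four it is about 34%, because each stratum contains two bands and nothing balances the arms within a band.

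**Effect on the primary comparison** (uniform ages, pain SD 17 mm, 30 per arm).
- Standard error of the difference = 17 × √(2/30) = 4.39 mm.
- SD of the age-driven shift, unstratified = r × 17 × √(2/30); with exact halving it is half of that.
- Power uses the normal approximation, with the SD reduced to 17 × √(1 − r²) under full age adjustment.

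| Assumed r | Unstratified | Stratified | Power, unadjusted | Power, age-adjusted (at most) |
|---|---|---|---|---|
| 0.1 | 0.44 mm | 0.22 mm | 84.2% | 84.5% |
| 0.2 | 0.88 mm | 0.44 mm | 84.2% | 85.6% |
| 0.3 | 1.32 mm | 0.66 mm | 84.2% | 87.4% |

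Even a 4-year gap would move the difference by only 4 × r × 17/9.52, which is 0.7 mm at r = 0.1 and 2.1 mm at r = 0.3.

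**The case against.** The strongest reply is that little harm follows. In a randomised trial a chance age gap does not bias the t-test, because its standard error already allows for such gaps. The plan says only that pain might change with age and gives no size for the association. The shifts above are small beside both the 4.39 mm standard error and the 13 mm target. A prespecified age covariate would meet the same concern in the primary comparison without touching allocation. All of this stands, and it limits the importance of the point. It does not rescue the plan as written, which contains no such covariate.

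It can also be said that the sentence is literally defensible, since no scheme guarantees identical age distributions. That is true in the strict sense: two strata leave chance differences within each stratum, and about a 34% chance of a lopsided band remains. But the sentence gives random assignment as the reason, and random assignment is compatible with balance on the strata used.

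A reader might infer that two envelope sets would halve the imbalance whatever the sample. The documents do not support that. The figure needs roughly uniform ages, a cut near the middle of the enrolled ages, and ordered opening; the documents give no age distribution and describe a random draw.

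**Conclusion.** The point holds in a limited form. The statement in Section 11.6 is wrong as a design statement, and the plan names age as a concern and then controls for it neither in allocation nor in the primary t-test. Stratifying would reduce the SD of the chance mean-age gap by about a third to a half with a median cut, and by about 20–48% with a cut at 34. It would lower the chance of a band at 5:10 or worse from about 58% to about 34%. These figures rest on assumed age shapes, blocks of four opened in order and, for the bands, 15 people in each.

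The benefit to the primary result is modest: an age-driven shift with an SD of about 0.4–1.3 mm now, for assumed correlations of 0.1–0.3. A reader might conclude that the unadjusted t-test is biased or invalid. It is neither. This is an inexpensive improvement and a correction of a false statement, not a threat to the trial's validity.

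**What to change.** 1. Delete the sentence in Section 11.6 that calls an even age spread unattainable.
2. In Section 10.1, replace the draw from a container with two sets of sealed, sequentially numbered envelopes, one per age stratum, each with its own permuted blocks. The next envelope in the set matching the recorded age is opened in order. Place the cut near the expected median age of lab attenders, and describe the same procedure in Section 13.1.
3. In Sections 11.1 and 11.6, prespecify age or the age stratum as a covariate in the primary comparison. If allocation is stratified, the stratum belongs in the model, because an unadjusted t-test would then be slightly conservative.

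If allocation is not to be changed, item 1 and an age covariate under item 3 are the minimum. Age is already collected, so that costs one sentence.

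The full change costs one extra envelope set, a switch from random drawing to ordered opening, and a short protocol edit before enrolment. Its downside is that incomplete last blocks can move the overall split one or two away from 30:30; in simulation with blocks of four it never moved by more than two.

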Similar data analysis will be included for pre-procedural anxiety.

Likert scale questions ("Overall, how satisfied were you with the use of Virtual Reality?" and "How likely would you be to request Virtual Reality if it were available for use?") will be reported in the final manuscript.

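### The planned age-band subgroup analysis contains no valid test of whether the VR effect differs by age; use one exploratory arm-by-age interaction with descriptive band tables instead

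*Combined protocol and SAP*

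**What the plan says.** Section 11.6 observes that randomisation cannot guarantee similar ages in the two arms and that pain perception may vary with age. It therefore plans "data tables comparing the average changes between those in different age groups", using the bands 18-25, 26-33, 34-41 and 42-50. It then adds: "A separate subgroup analysis will be performed comparing different age subgroups". The next paragraph states: "Similar data analysis will be included for pre-procedural anxiety".

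The section gives no subgroup test, interaction term, multiplicity rule or exploratory label. The only test named in sections 11.1, 11.5 and 11.6 is the two-sample t-test between arms. The sample size in 11.5 is built for that overall comparison alone: "To ensure a 2-sided α 0.05 and β 0.20, a minimum of 27 subjects are required for each arm". Section 11.4 enrols 30 per arm.

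**The concern.** The useful question about age is whether the VR effect, meaning the difference between VR and control, varies with it. The text has two natural readings, and neither answers that question.

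- **Bands compared with each other, arms pooled.** This shows whether older and younger people report different pain. It does not involve VR.
- **VR compared with control inside each band.** This gives four separate verdicts. One significant band beside one non-significant band is not evidence that their effects differ, but it is easily read that way.

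Two details add to the difficulty. The tables are described in terms of changes, yet procedural pain is rated once, after the draw (10.1, 10.2, 11.1). The only earlier pain rating is of expected pain, so a change from it would be a different endpoint from the primary one. Also, the anxiety analysis is tied to the pre-procedural score. Section 10.1 collects that score at screening, before the envelope is drawn, so VR cannot affect it.

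At stake is a reported age pattern that does not exist, or a method chosen after the data have been seen.

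**Working it through.** **Inputs from the documents.** Difference 13 mm, SD 17 mm, two-sided α 0.05, power 80%, 27 per arm needed (11.5); 30 per arm enrolled (11.4); four bands covering ages 18-50 (11.6). **Assumptions added here.** Ages evenly spread over 18-50, normal errors, independent bands. The documents give no age distribution and state no stratification by age.

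**1. The plan's own figure.** n per arm = 2 × (1.960 + 0.842)² × (17/13)² = 26.8, so 27. This reproduces the plan; the exact t-test calculation gives 28. Allowing for dropout, 54/0.90 = 60.

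**2. Size of a cell.** 30/4 = 7.5 per arm per band, or 27/4 = 6.75 after the assumed dropout.

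**3. Precision within a band.** At 7.5 per arm, SE = 17 × √(2/7.5) = 8.78 mm. The 95% half-width is t(13 df) × SE = 2.160 × 8.78 = 19.0 mm, which is wider than the 13 mm threshold.

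**4. Power within a band and the some-ages-only pattern.** Power p comes from the noncentral t distribution, with noncentrality 13 / (17 × √(2/n)). If the true effect is the same in all four bands, P(some but not all significant) = 1 − p⁴ − (1 − p)⁴.

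| n per arm per band | p | No band significant | All four | Some only |
|---|---|---|---|---|
| 6.75 | 25% | 31% | under 1% | 68% |
| 7 | 26% | 30% | under 1% | 70% |
| 7.5 | 28% | 27% | under 1% | 72% |
| 8 | 30% | 24% | under 1% | 75% |

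Simulation with random band sizes gives about 71%; with skewed ages it gives about 72%.

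**5. Sensitivity of the some-only figure at 7 to 8 per arm.**

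| True effect | SD | Some only |
|---|---|---|
| 8 mm | 17 | 42-46% |
| 10 mm | 17 | 53-58% |
| 20 mm | 17 | 85-87% |
| 13 mm | 20 | 59-64% |
| 13 mm | 25 | 47-51% |
| 13 mm | 30 | 39-42% |

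**6. No VR effect.** P(at least one of four bands significant) = 1 − 0.95⁴ = 18.5%.

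**7. What drives the pattern.** With 80% power in every band, 1 − 0.8⁴ − 0.2⁴ = 59% of trials would still show a mixed result. Larger cells would not remove it.

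**8. The alternative.** Fit one model with arm, age in years and arm × age. If ages are uniform over 18-50, the SD of age is 32/√12 = 9.24 years. The SE of the interaction slope is 17 / (√(60 × ¼) × 9.24) = 0.475 mm per year. A 13 mm change in effect across the range is 13/32 = 0.406 mm per year, a ratio to the SE of 0.855. On 56 df that gives about 13% power. A 26 mm change (ratio 1.71) gives about 39%. If the effect is constant, the test falsely signals an age difference in 5% of trials.

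**The case against.** The strongest objection is that the plan never says that VR will be tested within bands. Section 11.6 speaks of tables and of comparing age groups, and its stated motive is imbalance in age between arms. A reader might infer that the analysis as written will usually produce a false age-specific benefit. The documents do not support that: the 70-75% applies only if each band is tested separately, and then only for a constant effect near 13 mm with SD near 17. The SD is itself insecure, because 11.5 takes it from changes in pain among patients reporting a little more or a little less pain, not from a single post-venipuncture score. These points stand, and they are why the figure is conditional and shown with a range.

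Other parts of the objection also stand:

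- A reader might blame the small cells for the mixed pattern. Step 7 shows that separate testing produces it; small cells account for the wide intervals and low power.
- The 70-75% and the 5% are different kinds of quantity. The first is how often verdicts differ between bands, which becomes an error only if read as effect modification. The second is the size of a formal test.
- A reader might count the anxiety bands as four more chances of a false VR finding. The score named is a pre-randomisation baseline, so that count is not justified.
- The wording about changes may be loose usage for differences, since 11.1 also calls the 13 mm threshold a change.
- No decision rule in the plan uses the age tables.

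None of this supplies a method. Pooled bands say nothing about VR, and an interaction test, if intended, is not written. A purely descriptive intent is hard to square with a subgroup analysis listed in addition to the tables.

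**Conclusion.** The concern holds in a conditional form. Section 11.6 commits to comparing age subgroups but contains no valid test of whether the VR effect varies with age. If VR is tested separately in each band at the plan's 13 mm and 17 mm, with ages evenly spread, the results are 26-30% power, intervals of about ±19 mm and a spurious some-ages-only pattern in about 70-75% of trials. That share falls to roughly 40-50% for a smaller effect (8 mm) or a larger SD (25 to 30). With no VR effect, about 18.5% of trials have at least one falsely significant band.

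A trial of 60 cannot settle the age question by any method. The interaction model is better because it asks the right question once and shows its own imprecision, not because it is well powered. Severity is low to moderate: the primary t-test is unaffected, and nothing here casts doubt on it.

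**What to change.** In section 11.6:

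- Label the age analysis exploratory.
- Replace the band comparison with one model of post-procedure pain VAS on arm, age in years and arm × age. Report the interaction estimate with its 95% CI, and state that no VR-versus-control test is done within bands.
- State that power is low: about 13% for a 13 mm change in effect across ages 18-50 and about 39% for 26 mm. A non-significant interaction therefore does not show that the effect is equal at all ages.
- Keep the four-band table, giving counts, means and SDs by arm. Replace the reference to average changes with post-procedure pain VAS.
- For anxiety, apply the same model to post-procedure anxiety VAS, with pre-procedure anxiety as a covariate.

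The cost is a few lines of text and one regression per outcome. Sample size, data collection and the primary test do not change. The downsides are the assumption that the effect changes linearly with age and the low power of the interaction, both of which should be stated in the plan.
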